1.0 Background

This study is Part III of the Photodynamic Therapy-Induced Immune Modulation research. Part III is designed as a double-blinded proof of concept of feasibility study to define if the immunosuppression associated with photodynamic therapy (PDT) can be blocked by treatment with cyclo-oxygenase-2 (COX-2) inhibitor celecoxib in comparison to placebo. PDT consists of application of the photosensitizer 5-aminolevulinic acid followed by treatment with a blue light. PDT is used to treat pre-cancerous actinic keratosis on large areas of skin [1]. These studies are a continuation of ongoing studies that indicate that the lipid mediator platelet-activating factor (PAF) is generated in skin following PDT, and that PDT suppresses the immune system. **Our hypothesis is that PDT-generated PAF results in the immunosuppression associated with PDT.** Therefore, we propose that a treatment to block that immunosuppression could protect the patient undergoing PDT. Unfortunately, blockers of the PAF system are not currently commercially available. However our research studies using mice indicate that PAF- and PDT-induced immunosuppression is blocked by treatment with COX-2 inhibitors (2,3). We would like to conduct this research study **as a proof of concept.**

This double-blinded placebo-controlled study will test if a seven day treatment with COX-2 inhibitor celecoxib (200mg BID) following PDT will 1) block PDT-induced immunosuppression, and 2) enhance the effectiveness of PDT as measured by decreased numbers of actinic keratosis at 6 months and 12 months following PDT in comparison to placebo treated. This protocol will recruit subjects undergoing PDT or control subjects (not undergoing PDT) at Department of Dermatology at Boonshoft School of Medicine at Wright State University where the PI is Chair of Pharmacology & Toxicology, with joint appointment in the WSU Department of Dermatology. These studies are temporarily funded by WSU Department of Pharmacology and Toxicology.

Please note that this study will recruit both subjects who are planning to undergo PDT as a part of their management of their actinic keratosis and normal control subjects. This study will compare the effects of celecoxib vs placebo on the immune effects and effectiveness of PDT. This study also assesses if celecoxib alone modulates immune responses in control subjects. Thus, there will be 4 groups: PDT + Celecoxib, PDT + placebo, Control + Celecoxib and Control + placebo. We plan to randomize the subjects and one of the study personnel (coordinators who will not have any contact with subjects except for making up the medicines will be unblinded). These studies take advantage of the large numbers of patients undergoing PDT at WSU.

These studies include:

- Research subjects (those who receive PDT therapy)
 - Skin testing with intradermal Candida and Trichophyton antigens on two separate occasions.
 - Reporting a pain scale of 0-10
 - Urine collection (7 samples)
 - laboratory serum collection (2 venipunctures)
 - PDT-conducted for clinical reasons
 - 7 days of Celecoxib 200mg 2x per day or placebo
 - Follow up visits months 6 and 12 to assess actinic keratosis in treated areas.
- Control subjects

- Skin testing with intradermal Candida and Trichophyton antigens on two separate occasions.
- Urine collection (7 samples)
- Laboratory serum collection (2 venipunctures)
- 7 days of celecoxib 200mg 2 x per day or placebo.

2.0 Rationale and Specific Aims PART III

This protocol is designed to address multiple questions that have arisen since we have discovered that 1) PDT in mice generates PAF and related oxidized glycerophosphocholines (ox-GPCs); and that 2) PDT suppressed systemic immunity against the allergen DNFB (dinitrofluorobenzene) in wild-type but not PAF-R-knockout mice [3]; and 3) the literature indicates that PDT induces localized immunosuppression [4]; and 4) our ongoing studies that PDT of human subjects results in PAF agonists in their skin; and finally, 5) our ongoing studies that PDT of human subjects results in immunosuppression.

To test immunosuppression in humans, we plan two strategies. The first strategy will test skin testing against Candida and Trichophyton antigens, before and after PDT treatment.

We can also measure immune responses by taking peripheral blood mononuclear cells (PBMCs) from blood of subjects before/after PDT and incubate them with candida and trichophyton as well as other common antigens, to see if can measure an immune response (by measuring gamma-interferon by EIA). We can also measure levels of immunosuppressive T cells (Tregulatory cells) in the blood as well as the Treg-associated cytokine interleukin-10 (IL-10). Previously, we have demonstrated that when PAF is made, increased Tregs and IL-10 can be found in the mice. Again, our studies have demonstrated in mice that COX-2 inhibitors can block immunosuppression associated with PDT, and PAF agonists [2,3,4].

This study will also collect urine specimens from the PDT-treated subjects (before and after PDT) to test them for COX-2 metabolites and reactive-oxygen-associated markers (isoprostanes). We will also test urines in control subjects treated with celecoxib vs placebo.

We hypothesize that these studies will demonstrate the following:

1. PDT will result in immunosuppression (as measured by increased IL-10 in serum, and lymphocyte assays, as well as diminished candida/trichophyton skin testing).
2. PDT will result in increased COX metabolites and isoprostanes in urine.
3. Short-term Celecoxib treatment at commonly used dosages following PDT will inhibit the PDT-induced immunosuppression in comparison to placebo treatment.
4. Short-term Celecoxib treatment following PDT will block the increased COX metabolites in urine, but will have no effect on the isoprostanes.
5. Subjects undergoing PDT treated with celecoxib will exhibit decreased levels of erythema and decreased pain/tenderness in comparison to placebo control.
6. PDT will be more effective (as measured by less actinic keratosis in the PDT-treated areas at 6 and 12 mo following PDT) in those subjects who underwent Celecoxib treatment compared to placebo treatment.
7. Control (non-PDT) subjects will not experience any differences in immune responses in those treated with celecoxib versus placebo treatment.

This proof of concept study is valuable as it may form the basis of future studies to test if cyclooxygenase inhibitors can block PDT-mediated systemic immunosuppression, and potentially improve the long-term outcomes of PDT.

3.0 Inclusion/Exclusion Criteria

Inclusion Criteria for control subjects

- Adult age 45 or older
- Caucasion (Fair skin, Fitzpatrick types I and II)
- Ability to understand and consent to the instructions of the study
- Have access to stable transportation

Inclusion Criteria for study subjects

- WSU dermatologist has prescribed PDT for the treatment of actinic damage (Presence of precancerous actinic keratoses whose treatment necessitates PDT with the BLU-U).
- Undergoing PDT on greater than 5% body surface area: face and scalp, face and dorsal surface of arms, face and chest, face and back, or dorsal surface of arms alone, chest alone, or back alone.
- Caucasian (Fair skin, Fitzpatrick types I and II)
- Adult-age 45 or older
- Ability to understand the informed consent and comply with instructions and have stable transportation.

Exclusion Criteria for all subjects

- PDT on less than 5% body surface area (eg, forehead)
- Present treatment with corticosteroids or Non-steroidal anti-inflammatory drugs (e.g., cyclooxygenase inhibitors) within past 2 months (except low-dose 81 mg aspirin).
- On antioxidant supplements (e.g., vitamin C) for past 2 months
- Tanning bed use within last 3 months
- PDT treatments within last 3 months
- Significant health issues that could affect your immune system (e.g., uncontrolled Diabetes Mellitus, Rheumatoid arthritis, skin rashes, psoriasis) that could interfere with testing
- Pregnant or nursing
- No immunosuppression, and on no immunosuppressive medications or NSAIDS within past 30 days (except low-dose [81 mg daily] aspirin).
- No significant underlying diseases that could potentially interfere with the immune assays or cardiac or renal or liver problems.
- History of blood clot or hypercoagulable state or GI bleed/ulceration.

All subjects will be asked the screening questions below as part of the inclusion/exclusion criteria:

- Are you 45 years old or older?
- Do you regularly use tanning beds?

- Are you being treated for anything that requires UV-treatments?
- Have you had any diseases that got worse when you went in the sun?
- Are you using topical or oral anti-inflammatory doses of NSAIDS or steroid?
- Have you ever had any abnormal reactions or allergies to NSAIDS?
- Are you taking any medications that warn you to stay out of the sun?
- Have you ever had a reaction to medications that were applied to your skin?
- Do you have severe sugar diabetes, heart problems or liver problems or other health problems that affect your immune system?
- Have you had significant sun exposure or sunburn within the last 2 weeks? Tanning bed exposure in the past 3 months?
- Have you had PDT in past 3 months?
- Have you ever had a blood clot or other bleeding issues?
- Have you ever had a stomach ulcer or bleeding from GI tract?
- Are you pregnant or nursing?

[figure not shown]
4.0 Enrollment

Subjects who will be undergoing PDT for actinic keratoses and controls will be recruited from the Dermatology clinics at WSU. Control subjects may also be recruited from other sites or other practices. The potential subjects will be told by their physician about the study. They will be reminded that this study will in no way benefit them directly and that their participation is only voluntary, and if they choose not to participate it will not impact their care or the interest of their providers in their case. In addition, advertising flyers placed in the Wright State Department of Dermatology clinics will be used to seek PDT subjects and control subjects. The flyers will require subjects who are interested in participating in the study to contact the PI, or the research office. The PI, or study team member, will meet with the potential subjects. The PI will determine enrollment status based on the inclusion and exclusion criteria. Each subject will be given all of the procedures and risks in writing and a signed informed consent statement will be obtained from each subject prior to enrollment in the study. The subjects will also be informed of the need to avoid sun exposure or tanning bed use for 3 months prior to PDT or during the study.

5.0 Study Procedures

Outlines of testing for PDT-treated subjects. Please note that the Controls (see picture on page 9) will undergo all procedures EXCEPT the PDT. Controls also will not have actinic keratosis counted/mapped and will not be following up to have actinic keratosis mapped at 6 and 12 months.

PDT Testing Protocol

DAY -2. Consent, Skin testing, Venipuncture

- Informed consent. Explanation of the study, listing of all the required dates to return to the clinic for the study, and a signed informed consent will be obtained
- Intended PDT treatment site will be noted, photographed and recorded
- Actinic keratosis mapping. Numbers of AKs will be counted and mapped on a diagram to allow us a base recording for future comparisons
- Venipuncture. 20ml of blood will be drawn by routine phlebotomy.
- Intradermal skin testing application. An area on inner (volar) arm where planned PDT will not be taking place will be photographed, and intradermal injections of 0.1 ml standardized solutions of commercially available Candida and Trichophyton protein antigens, or saline will be intradermally injected into skin to form small wheals. The area will be photographed.

DAY 0. Read skin testing results, Urine specimen, PDT, Start celecoxib or placebo

- Intradermal skin testing reading. The skin reactions to the Candida and Trichophyton antigens will be visualized, photographed, and the size of the reactions measured using calipers.
- Urine specimens. Urine Sample will be obtained, and 6 sterile pre-labelled urine cups will be provided to the subject for home urine collection along with an orange opaque biohazard bag to store the samples in the freezer until they are returned to the research site.
- Photodynamic Therapy (PDT). PDT is a standard treatment at the WSU Department of Dermatology clinics and approximately 75-80 procedures are performed annually. PDT is being conducted for clinical reasons and will therefore be submitted to the patient/patient's insurance as routine care. **Patients sign a separate informed consent for the PDT therapy** and the PDT will follow standard clinical guidelines. Control subjects will not undergo the PDT treatment.
- Celecoxib. The subjects in the study arms which receive Celecoxib will be provided #14 capsules of 200mg celecoxib or 14 placebo capsules and instructed to take 1 capsule in the morning and 1 capsule in the evening. They will be instructed to start the medication the same day (2 doses) and take as prescribed for a total of seven days. The subjects will be provided a 7 day pill dispenser with AM/PM components for their use. Funds from the study budget

will pay for the prescription so that there will not be a cost to the subjects. The dose of celecoxib was similar to that used long-term in previously reported studies where subjects were treated with celecoxib 200mg BID for ~ 1 year. This is a dose and time frame that based upon our murine studies, should inhibit PAF-induced immunosuppression.

DAY 1-5 Urine Home Collection

At night (~8 h post-PDT) on the day of PDT treatment, and days 1-5 First morning urine samples will be obtained in the sterile cups provided to the subject, each placed in the biohazard bag and stored in the freezer. The subject will bring the urine samples back to the research clinic at day 7 study visit. Subjects will be asked to fill out a Urine Collection Record form. Also, they will rate the pain associated with the PDT treatment on the Skin Pain Visual Analogue Scale (VAS). The scale will be 0 (no skin pain) to 10 (severe skin pain).

DAY 7. Return of urine samples, Repeat skin testing to control and PDT-treated sites, Venipuncture.

- Urine samples returned to the research site from research subjects
- Subjects will bring empty pill dispensers.
- Intradermal skin testing application. An area on opposite inner (volar) arm where PDT did not take place, as well as a PDT-treated site (extensor arms, scalp, etc) will be photographed, and intradermal injections of 0.1 ml standardized solutions of commercially available Candida or Trichophyton protein antigens, or saline will be intradermally injected into skin to form small wheals. The areas will be photographed.
- Reporting amount of pain. The 0-10 pain scale will be used again to query the subject as to amount of discomfort in the PDT-treated sites.
- Venipuncture. 20ml of blood will be drawn by routine phlebotomy.

DAY 9. Read skin testing results

[figure not shown]
- Intradermal skin testing reading. The skin reactions to the Candida and Trichophyton antigens will be visualized, photographed, and the size of the reactions measured using calipers.

6 months and 12 months.

The subjects who were treated with PDT will be seen when they return to the dermatology clinic for their routine follow up care. We will use a body map to record the current numbers and sites where they have the precancerous AK lesions. Their current numbers and sites will be compared to the numbers and locations of their AKs pre-treatment with PDT obtained at visit Day 0. This comparison will help to define effectiveness of the therapy. This information will become part of their medical record.

CONTROL SUBJECTS

CONTROL Testing Protocol

DAY 0. Consent, Skin testing, Venipuncture, Urine specimen

- Informed consent. Explanation of the study, listing of all the required dates to return to the clinic for the study, and a signed informed consent will be obtained
- Venipuncture. 20ml of blood will be drawn by routine phlebotomy.
- Intradermal skin testing application. An area on inner (volar) arm will be photographed, and intradermal injections of 0.1 ml standardized solutions of commercially available Candida or Trichophyton protein antigens, or saline will be intradermally injected into skin to form small wheals. The area will be photographed.
- Urine specimens. Urine Sample will be obtained, and 6 sterile pre-labelled urine cups will be provided to the subject for home urine collection along with an orange opaque biohazard bag to store the samples in the freezer until they are returned to the research site.

DAY 2. Read skin testing results, Start celecoxib or placebo

- Intradermal skin testing reading. The skin reactions to the Candida and Trichophyton antigens will be visualized, photographed, and the size of the reactions measured using calipers.
- Celecoxib. The subjects in the study arms which receive Celecoxib will be provided #14 capsules of 200mg celecoxib or 14 placebo capsules and instructed to take 1 capsule in the morning and 1 capsule in the evening. They will be instructed to start the medication the same day (2 doses) and take as prescribed for a total of seven days. The subjects will be provided a 7 day pill dispenser with AM/PM components for their use. Funds from the study budget will pay for the prescription so that there will not be a cost to the subjects. The dose of celecoxib was similar to that used long-term in previously reported studies where subjects were treated with celecoxib 200mg BID for ~ 1 year. This is a dose and time frame that based upon our murine studies, should inhibit PAF-induced immunosuppression.

DAY 9. Repeat skin testing, Venipuncture.

- Subjects will bring empty pill dispensers.

- Intradermal skin testing application. An area on opposite inner (volar) arm where previous skin testing did not take place will be photographed, and intradermal injections of 0.1 ml standardized solutions of commercially available Candida or Trichophyton protein antigens, or saline will be intradermally injected into skin to form small wheals. The areas will be photographed.
- Venipuncture. 20ml of blood will be drawn by routine phlebotomy.

DAY 11. Read skin testing results

- Intradermal skin testing reading. The skin reactions to the Candida and Trichophyton antigens will be visualized, photographed, and the size of the reactions measured using calipers.

Compensation.

The subjects will be compensated for involvement in the study.

Research subjects require more visits and procedures than control subjects.

Breakdown for each event is as follows:

Consent	\$20.00	PDT (\$20), Control (\$20)
Venipuncture	\$10.00	PDT (\$20), Control (\$20)
Urine collection	\$5.00	PDT (\$35), Control (\$35)
Skin testing APPLICATION	\$15.00	PDT (\$45), Control (\$45)
Skin testing READING	\$20.00	PDT (\$40), Control (\$40)
Bonus for completing study	\$65.00	PDT (\$65), Control (\$65)
Follow up visits at 6 and 12 months	\$25.00	PDT (\$50)

Hence the research (PDT) subjects may receive up to **\$ 275.00** and the control subjects up to **\$225.00**.

There is no cost for parking at the Wright State Physician's Building. Compensation is based upon completed study procedures and overall study completion. Since completion of study procedures are critical to the study findings if a subject cannot come to their scheduled visit (and cannot be quickly rescheduled) they will be removed from the study. Another subject will be enrolled in their place. Our goal is to enroll 48 subjects who complete the study.

6.0 Reporting of Adverse Events or Unanticipated Problems involving Risk to Participants or Others

Risks of the study are as follows:

1. Photodynamic therapy. The risks to PDT are explained to the patient at the time of therapy decision and obtaining the informed consent for that standard of care procedure. PLEASE NOTE THAT PDT TREATMENT IS ALREADY RECOMMENDED FOR THE TREATMENT OF THE SUBJECT. THEY WILL BE SIGNING A SEPARATE INFORMED CONSENT FOR THE TREATMENT AND THEY/THEIR INSURANCE AS APPROPRIATE WILL BE BILLED FOR THE TREATMENT.
2. Photography - the risk of photography is the possible loss of confidentiality. Pictures will not be of recognizable body parts or markings. Photos will be

labeled with the study number and a code that does not identify the subject. Photos will not include any identifying information.

3. Urine samples/non-invasive skin measurement with calipers. There are no risks to these.
4. Intradermal skin testing. These procedures are used in dermatology and allergy to define the ability of a host to respond to the allergen of interest. The majority of individuals will test positive to Candida protein antigens, and approximately 50% of individuals test positive for antigens from the common dermatophyte fungus Trichophyton (which causes skin infections like “athlete’s feet”). The side effects are localized skin inflammation and rash and occasionally can be painful. Very rarely an individual can have a systemic reaction. If we do note that the subject’s first skin testing results in exaggerated reactions, then the subject will not undergo further testing with this antigen.
5. Celecoxib Celecoxib is a commonly used NSAID, which is COX-2 specific. It was designed to have anti-inflammatory effects but have minimal side effects such as gastric distress, etc. There have been multiple studies examining the long-term effects of celecoxib 200mg BID. In particular, there was a published multicenter trial that indicated that long-term celecoxib was effective for diminishing the incidence of non-melanoma skin cancers [7]. It should be noted that in these studies the incidence of side effects of the celecoxib was similar to placebo. Long-term use of COX-2-selective inhibitors have been associated with increased cardiovascular events due to a pro-coagulant effect [6]. However, this is not associated with short-term use. There is a slight risk of GI bleeding. These effects will be minimized as we will recruit subjects with no history of GI ulceration/bleeding/blood clots.
6. There is also the potential risk of loss of confidentiality, but this will be minimized as photos of the PDT- and treated sites will not allow the person to be identified, and will not expose buttocks/genitals. Samples will be labeled with numeric numbers --III-001, III-002, III-003 etc. and the study number (XXXX). Example III-001-XXXX.

Risks of exaggerated PDT-related sunburn will be minimized as subjects will be queried about abnormal reactions to sun or artificial sources of light, as well as if they are taking any medicine which is potentially photosensitizing.

Adverse Event and Serious Adverse Event Collection and Reporting

Information related to any adverse event will be collected at every study visit. The NCI-CTCAE (Common Terminology Criteria for Adverse Events) volume 4.03 published June 14, 2010 will be utilized for definition, grading scale and ‘study relatedness’ criteria of the event. [name] will be responsible for determining whether an AE is expected or unexpected. An AE will be considered unexpected if the nature, severity, or frequency of the event is not consistent with the risk information previously described for the study intervention.

An adverse event (AE) means any untoward medical occurrence in a subject associated with the use of an intervention that does not necessarily have a causal relationship with the intervention. It can be any unfavorable and unintended sign (including abnormal laboratory findings), symptom or disease temporally associated with the investigation, whether or not considered intervention-related.

An unanticipated problem can be any unexpected, related or possibly related to the intervention, and increases risk to participants or others more than was previously known. All three must be true to have an unexpected problem. Each unanticipated problem is assessed as to the impact on subject safety.

A serious adverse event (SAE) is any AE that results in one of the following outcomes:

- Death
- Life threatening
- Requires hospitalization or prolonged hospitalization
- A congenital anomaly/birth defect
- Persistent or significant disability/incapacity
- Requires intervention to prevent permanent impairment or damage

All reports will simultaneously be submitted to NIAMS, through KAI. This will include:

- Safety reports and meeting deliberations, including findings of adverse events and any comments, minutes, or recommendations resulting from the review of these periodic reports or meetings.
- Expedited reporting, including SAEs and unanticipated problems, along with the independent assessment of such events, as appropriate, should be reported in an expedited manner.

Each AE will be accompanied with the severity grade. The grades are as follows:

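### The 6- and 12-month AK counts are compared with the pre-PDT map with no record of, or rule for, lesions treated in between, so a lesion cleared by later care would score as PDT success

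*Combined protocol and SAP*

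**What the plan says.** Hypothesis 6 in section 2.0 expects celecoxib to improve PDT, judged by "less actinic keratosis in the PDT-treated areas at 6 and 12 mo following PDT". Section 8.0 lists the AK numbers at both times among the study outcomes.

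Section 5.0 sets out how the data arise. Before PDT: "Numbers of AKs will be counted and mapped on a diagram to allow us a base recording for future comparisons". For follow-up: "The subjects who were treated with PDT will be seen when they return to the dermatology clinic for their routine follow up care". At those visits: "We will use a body map to record the current numbers and sites where they have the precancerous AK lesions". Then: "Their current numbers and sites will be compared to the numbers and locations of their AKs pre-treatment with PDT". The same section says this comparison helps to define how effective the therapy was, and that the information goes into the medical record.

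The documents do not address three things: whether the map is completed before any lesion is treated at the visit, whether AK treatment in the PDT field after Day 0 is recorded, and how a treated lesion enters the comparison. The 3-month exclusion for prior PDT in section 3.0 applies at entry only. Section 8.0 names McNemar's test, paired t-tests and exact or non-parametric alternatives, but has no rule for interim treatment.

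**The concern.** A count of lesions present today measures the effect of PDT only if nothing else has removed lesions since. Here the count is made in the service that manages these lesions. A lesion that survived PDT, was treated at or around the 6-month visit and cleared would be missing from the 12-month map. Under the stated comparison it could not be told apart from a lesion that PDT cleared. The same applies at month 6 to any treatment given between PDT and that visit, or at the visit itself before mapping.

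What is at stake is hypothesis 6, particularly at month 12. Similar 12-month counts could mean that celecoxib brought no lasting benefit, or that later care removed the surplus lesions in the placebo arm. Section 8.0 also says that data from this study will feed a power analysis for possible further work, so a distorted effect would carry forward.

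**Working it through.** **The plan's own figures.** Section 8.0 gives 12 per group in four groups: 4 × 12 = 48, which agrees with the 48 completers in section 5.0. The AK contrast concerns PDT subjects only, so it is 12 versus 12. The 12 comes from a pilot rule of thumb. No effect size, SD, alpha or power is given for AK counts, so there is no stated power to reproduce, and everything below is illustration on assumed inputs.

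**Effect on the arm difference.** Let R be the mean number of AKs remaining at 6 months, q the fraction of these treated and cleared before month 12, and N the mean number of new lesions, taken as equal in both arms. Then:

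- 12-month mean = R(1-q) + N
- arm difference (celecoxib minus placebo) = Rc(1-qc) - Rp(1-qp)

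Assume Rp = 6 and Rc = 3, a true difference of -3.0.

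Same q in both arms, so the difference is -3.0 × (1-q):

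| q | Difference |
|---|---|
| 0 | -3.0 |
| 0.25 | -2.25 |
| 0.50 | -1.5 |
| 0.75 | -0.75 |
| 0.90 | -0.3 |

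On the ratio scale with N = 0, the ratio stays at 3(1-q)/6(1-q) = 0.50. With N = 2 it moves toward 1: 5/8 = 0.625 at q = 0, 3.5/5 = 0.70 at q = 0.5, and 2.3/2.6 = 0.885 at q = 0.9.

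Unequal q:

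- placebo 0.75, celecoxib 0.50: 3 × 0.50 - 6 × 0.25 = 0 (effect vanishes)
- placebo 0.75, celecoxib 0.25: 3 × 0.75 - 6 × 0.25 = +0.75 (reversed)
- placebo 0.30, celecoxib 0.90: 3 × 0.10 - 6 × 0.70 = -3.9 (exaggerated)

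If treated lesions are recorded and counted as not cleared, each arm returns to R(1-q) + Rq + N = R + N, and the difference returns to -3.0 whatever the fractions.

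**Effect on power.** Simulation with 12 per arm, a two-sample t-test at an assumed two-sided 0.05, negative binomial counts with means 6 and 2.5 and dispersion k = 4, no new lesions, and the same q in both arms:

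| q | Power |
|---|---|
| 0 | about 0.79 |
| 0.35 | about 0.70 |
| 0.45 | about 0.64 |
| 0.70 | about 0.47 |
| 0.90 | about 0.20 |

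The result depends on the model. A second simulation used a baseline mean of 12 AKs, residual means of 6 and 3, and no new lesions. At q = 0, 0.5 and 0.75, power for the 12-month count was 0.62, 0.47 and 0.30; for change from baseline it was 0.32, 0.09 and 0.06. Change from baseline loses more in relative terms because treating lesions does not reduce the baseline variance it carries.

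**The case against.** The strongest objection is that the mechanism is not in the documents. They say that subjects return for routine follow-up and are mapped; they do not say that any AK is treated at or between those visits. This stands. Interim treatment is an inference, and the point must be put conditionally.

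A reader might go further in four ways that the documents do not support.

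- **That the celecoxib effect is necessarily pulled toward zero.** Shrinkage is the expected direction for the absolute difference under blinded care with similar treatment rates. With equal rates and no new lesions the ratio does not move, and unequal rates can push the difference either way.
- **That power collapses by a known amount.** Holding the SD fixed at a 1.2 SD effect, the noncentral t with 12 per arm gives 0.80 undiluted, 0.34 when 55% of the effect remains and 0.06 when 10% remains. Clearing lesions also reduces the variance of the counts, however, and at the same fractions the simulated power of the count itself is about 0.64 and 0.20. The plan claims no power for this outcome in any case.
- **That the data would be beyond recovery.** Treatment given in the same clinic could probably be abstracted from the chart later. What may be lost is treatment given elsewhere and the correct count at a visit where lesions were treated before mapping.
- **That month 6 ought to be the main comparison.** It is the cleaner time point, since it is not exposed to treatment given after its mapping, but hypothesis 6 and section 8.0 name both times and ranking them is a preference. A cumulative endpoint starting from the month-6 map would miss treatment between Day 0 and month 6.

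The stakes are also modest: this is a proof-of-concept study and AK count is one of four listed outcomes. That limits the weight of the point, but the gap remains.

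**Conclusion.** The point holds in conditional form. The plan compares current AK counts from routine-care visits with the pre-PDT map and has no order of mapping and treatment, no record of interim AK treatment and no counting rule. If such treatment occurs, PDT-surviving lesions that it clears are scored as PDT success. At a common treated-and-cleared fraction q the absolute arm difference is multiplied by (1-q); with differing fractions the bias can take either direction.

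Neither q, the number of new lesions nor the variance of the counts is given, so the size cannot be fixed from the documents. The range runs from no loss, if nothing is treated, to a severe loss, if most residual lesions are cleared. The change is worth making because it is cheap and the information is best collected as events occur.

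**What to change.** 1. Complete the AK map at each follow-up visit before any lesion is treated at that visit.
2. Add columns to the body map for the date, site, number and type of any AK treatment in the PDT field from Day 0 to month 12, filled from the chart and by asking the subject, so that care given elsewhere is captured.
3. State in section 8.0, before unblinding, that in the 6- and 12-month comparisons lesions treated in the field since PDT are counted as not cleared, with the as-observed count as a sensitivity analysis.

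While editing this text, reconcile the baseline date: section 5.0 schedules the AK map at Day -2, but its follow-up paragraph places the pre-treatment map at Day 0.

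The cost is a few form columns, some chart abstraction and a short addition to the analysis text. The one statistical drawback is that a treated lesion that might have regressed without treatment is counted as persisting; the sensitivity analysis shows how much this matters. No change to patient care is proposed.
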